## 7.2 Efficacy Assessments

There are two primary efficacy endpoints. Other secondary and exploratory efficacy endpoints are tested to better understand the potential clinical benefit of C213 on cluster headache subjects.

## 7.2.1 Co-primary Efficacy Endpoints

#### 7.2.2 Pain Relief

One of the co-primary efficacy endpoints is the proportion of subjects who achieve pain relief at 15 minutes post patch administration. Headache pain will be assessed using a 4-point scale (0 = none, 1 = mild, 2 = moderate, 3 = severe), with pain relief defined by a decrease in pain from severe to mild or none, without the use of acute rescue medication within 15 minutes post patch administration. Subjects record their answers in the eDiary to the question: "How bad is your headache pain?". Subjects are also asked in the eDiary, "Did you take any medication, since your last diary entry, other than the patches you applied to treat your headache?" in order to assess rescue medication use (see section 7.2.4.4).

#### 7.2.3 Sustained Pain Relief

The other co-primary efficacy endpoint is the proportion of subjects who achieve sustained pain relief from 15 minutes to 60 minutes post patch administration. Sustained pain relief requires a pain rating of mild or none at each timepoint from 15 minutes to 60 minutes without the use of acute rescue medication at any time during the 60 minutes post patch administration.

Protocol: CP-2019-001 Page 16 of 26

Final Version 1.0

## 7.2.4 Secondary Efficacy Assessments

#### 7.2.4.1 Pain Freedom

Pain freedom is defined by a rating of none using the 4-point scale (0 = none, 1 = mild, 2 = moderate, 3 = severe) without the use of acute rescue medication up until the timepoint being assessed (10 or 15 minutes).

#### 7.2.4.2 Sustained Pain Freedom

Sustained pain freedom requires a pain rating of none at each timepoint from 10 (or 15) minutes to 60 minutes without the use of acute rescue medication at any time during the 60 minutes post patch administration.

#### 7.2.4.3 Pain Relief and Sustained Pain Relief

Secondary endpoints of pain relief (at 5, 10, 20, and 30 minutes post patch administration) and sustained pain relief (5 and 10 minutes to 60 minutes post patch administration) will be assessed in the same manner as the primary endpoints. For example, pain relief at 5 minutes requires a rating of mild or none without the use of acute rescue medication within 5 minutes post patch administration. Sustained pain relief requires a pain rating of none at each timepoint from 5 (or 10) minutes to 60 minutes without the use of acute rescue medication at any time during the 60 minutes post patch administration.

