## Secondary efficacy endpoints:

- Proportion of subjects that achieve pain relief at 5, 10, 20 and 30 minutes post patch application
- Proportion of subjects that achieve sustained pain relief from 5 to 60 minutes and from 10 to 60 minutes post patch application
- Proportion of subjects that achieve pain freedom at 10 and at 15 minutes post patch application
- Proportion of subjects that achieve sustained pain freedom from 10 to 60 minutes and from 15 to 60 minutes post patch application
- Proportion of subjects using rescue therapy within 20 minutes post patch application
- Proportion of subjects able to perform their usual daily activities as assessed by the subject at 5, 10, 15, 20, 30 and 60 minutes post patch application

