## 7.1.3 Methods for Handling Missing Data

Missing pain and daily activities data for participants in the mITT population will be imputed via last observation carried forward (LOCF). Prior to imputing missing endpoint data for the endpoint sustained pain relief 15-60 minutes, pain relief will be assessed at each of the 15, 20, 30, and 60-minute timepoints that have data available. If any of these

Protocol: CP-2019-001 Page 15 of 26

Final Version 1.0

timepoints has a pain severity rating of moderate or severe, or if the subject has used a rescue medication/therapy, then the subject will be considered to have not achieved sustained pain relief and this endpoint will not be imputed. Otherwise, missing pain data will be imputed using LOCF. Missing data for all sustained pain relief and sustained pain freedom endpoints will be handled this way.

Missing safety data will not be imputed. Due to COVID-19, it is unavoidable that some subjects will be missing certain safety assessments, such as (but not limited to) Visit 3 clinical labs, vital signs, and ECG. This is because the Visit 3 occurred during the pandemic and telemedicine visit was necessary. Safety summaries will be generated using observed data, and missing safety assessments will be captured as protocol deviations.

Missing rescue medication data will be handled as described in section 7.2.4.4.

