### 12. CHANGES FROM PLANNED ANALYSIS

Due to insufficient enrollment numbers, the CMH test as described in the protocol for the primary and secondary analyses will not be performed. The protocol also describes a fixed sequential procedure to control for overall type 1 error. This will not be implemented since the actual number of randomized subjects is quite a bit less than planned and the pre-specified statistical analyses as described in the protocol cannot be performed.

Protocol: CP-2019-001 Page 25 of 26

Final Version 1.0

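### SAP 7.2.4.3 defines secondary sustained pain relief with the pain-freedom threshold, so the 10-60 minute endpoint would duplicate sustained pain freedom 10-60

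*SAP*

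**What the plan says.** SAP 7.2.4.3 covers the secondary relief endpoints in three steps.

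- It opens by saying that they "will be assessed in the same manner as the primary endpoints".
- It then gives an example: "pain relief at 5 minutes requires a rating of mild or none without the use of acute rescue medication".
- It closes with the rule for the sustained version: "Sustained pain relief requires a pain rating of none at each timepoint from 5 (or 10) minutes to 60 minutes", with no rescue during the 60 minutes.

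The definitions around it are:

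- **Primary sustained relief, SAP 7.2.3:** "Sustained pain relief requires a pain rating of mild or none at each timepoint from 15 minutes to 60 minutes". SAP 2.2.1 and protocol 5.1 and 7.4.1 use the same threshold.
- **Sustained pain freedom, SAP 7.2.4.2:** "Sustained pain freedom requires a pain rating of none at each timepoint from 10 (or 15) minutes to 60 minutes", also with no rescue during the 60 minutes.
- **Endpoint list, SAP 2.2.1:** sustained relief (5-60, 10-60) is listed separately from freedom, which reads "Proportion of subjects that achieve sustained pain freedom from 10 to 60 minutes and from 15 to 60 minutes post patch application".
- **Missing data, SAP 7.1.3:** a subject fails sustained relief 15-60 if any of the available "timepoints has a pain severity rating of moderate or severe, or if the subject has used a rescue medication/therapy". The same handling is extended to all sustained relief and sustained freedom endpoints.
- **Secondary analyses, protocol 7.4.2:** methods are to be similar to those for the primary endpoints.

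**The concern.** The closing sentence of SAP 7.2.4.3 is the only explicit rule for deriving these two endpoints, and it contradicts the opening sentence of its own paragraph. Two programmers could produce different results, each citing the SAP.

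Three things go wrong if the sentence is followed as written.

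- Sustained relief 10-60 is reported as a second copy of sustained freedom 10-60, and the intended endpoint is not reported at all.
- Sustained relief 5-60 becomes sustained freedom 5-60. Freedom is defined only from 10 and from 15 minutes, so this endpoint appears in neither document.
- The 5-60, 10-60 and 15-60 relief endpoints should differ only in how early relief begins. Read literally, moving from 15-60 to 10-60 also tightens the pain threshold, so onset and depth of relief are confounded.

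**Working it through.** The plan gives no numerical result for these endpoints, so there is no figure of its own to reproduce on this point. The sample size (SAP section 5) rests on the co-primary endpoints and does not depend on it.

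**Inputs.** The pain scale is 0 to 3 (SAP 2.2.1). Post-dose ratings are at 5, 10, 15, 20, 30 and 60 minutes (protocol 6.1.3.1). Any rescue within 60 minutes is failure (SAP 7.2.3 to 7.2.4.3). Missing scores follow SAP 7.1.3: fail on any observed moderate or severe score in the window, otherwise carry the last observation forward.

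**Step 1: compare the rules for 10-60 minutes.**

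| Element | Relief 10-60, literal 7.2.4.3 | Relief 10-60, as primary | Freedom 10-60, 7.2.4.2 |
|---|---|---|---|
| Score required | 0 | 0 or 1 | 0 |
| Timepoints | 10, 15, 20, 30, 60 | same | same |
| Rescue | none in 60 min | none in 60 min | none in 60 min |
| Missing data | 7.1.3 | 7.1.3 | 7.1.3 |

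The first and last columns are identical.

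**Step 2: confirm by enumeration.**

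- Complete data: 4^6 × 2 (rescue yes/no) = 8,192 patterns. Literal relief 10-60 and freedom 10-60 disagree in 0; each is met by 4. Under mild or none, relief 10-60 is met by 128.
- Missing scores allowed, at least one score by 15 minutes: (5^6 − 5^3) × 2 = (15,625 − 125) × 2 = 31,000 patterns. Disagreements: 0; each is met by 96. Under mild or none: 972.

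So the missing-data rule does not separate the two endpoints either.

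**Step 3: how much the definition narrows** (complete scores within the window, no rescue).

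- 10-60, five timepoints: 2^5 = 32 qualifying patterns under mild or none, 1 under none.
- 5-60, six timepoints: 2^6 = 64 against 1.

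These counts describe definitions. They are not expected response rates.

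**Step 4: one subject.** Scores at 5, 10, 15, 20, 30 and 60 minutes are 2, 1, 0, 0, 0, 0, without rescue. The subject achieves relief at 10 minutes, sustained relief 15-60 and sustained freedom 15-60. Sustained relief 10-60 is met under mild or none and failed under the literal rule.

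**Step 5: effect on proportions.** Let p be the proportion with sustained relief under mild or none, and q the share of those responders who rate mild at least once in the window. The literal rule reports p(1−q). The documents do not give q; over 0 to 1, q = 0 changes nothing, q = 0.5 loses half of responders and q = 1 loses all.

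**Step 6: effect on the comparison.** The difference moves from p1 − p0 to p1(1−q1) − p0(1−q0). Borrow the planning rates of 55% and 20% purely for illustration (the SAP states them for the co-primary endpoints), giving a difference of 0.35:

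- q1 = q0 = 0.5: 0.275 − 0.100 = 0.175.
- q1 = 0.5, q0 = 0: 0.275 − 0.200 = 0.075.
- q1 = 0, q0 = 0.5: 0.550 − 0.100 = 0.450.

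Each arm's proportion can only stay equal or fall, but the difference can move either way.

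**The case against.** The strongest reply is that a careful reader can recover the intent. The opening sentence and the 5-minute example both point to mild or none, relief and freedom are listed separately, and freedom has its own subsection. No program or output in the documents shows that the literal rule was used. That is fair, and the sentence is most likely carried over from 7.2.4.2. It does not remove the problem: the slip sits in the operative rule of a final SAP.

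The protocol writes the mild-or-none rule for sustained relief only for 15-60 minutes and merely lists 5-60 and 10-60. This limit stands. The conflict with the protocol follows from its general definition of pain relief and from protocol 7.4.2; the conflict inside the SAP is direct and sufficient.

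Two pieces of supporting evidence are weak. The failure rule in SAP 7.1.3 is written for 15-60 and then applied to freedom endpoints as well, so it does not settle the threshold. SAP section 12 reports that "Due to insufficient enrollment numbers, the CMH test as described in the protocol for the primary and secondary analyses will not be performed" and that the fixed sequence is dropped, and it mentions no change to this definition. But section 12 is not exhaustive: it does not name the odds ratios and confidence intervals in protocol 7.4.1, which are absent from SAP 9.1.

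The decision impact is also limited. Enrollment fell well short, and with no multiplicity procedure (SAP 7.1.1 and section 12) these endpoints gate no other test. That bears on priority, not on whether the text is wrong.

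**Conclusion.** The point holds. SAP 7.2.4.3 gives two incompatible thresholds for sustained relief 5-60 and 10-60, and the explicit one is the pain-freedom threshold. The duplication of the 10-60 endpoints under the literal reading is exact and needs no assumption about the data.

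The scope is two secondary endpoints at two doses, or four Fisher comparisons with placebo. The co-primary, single-timepoint relief and pain-freedom endpoints are unaffected. The numerical effect on the reported proportions depends on the unknown q, and the effect on treatment differences depends on q in each arm, so neither its size nor its direction can be stated from the documents. It should be fixed, but it does not threaten the primary analysis.

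**What to change.** In the last sentence of SAP 7.2.4.3, change the required rating from none to mild or none for sustained pain relief from 5 (or 10) to 60 minutes. Do this as a dated SAP amendment before unblinding. Then check that both derived variables use that threshold and that sustained relief 10-60 is not coded as sustained freedom 10-60; a test record with the scores in Step 4 separates the two rules.

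The SAP is dated 14APR2021, and the documents do not show when the database was locked or unblinded. If unblinding has passed, issue a dated clarification stating which rule was programmed, and carry it into the study report.

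The cost is one phrase and a check of two variables. No new data are needed, and sample size and conduct do not change.

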## 7.2.4.4 Rescue Medication/Therapy Use

A subject is considered to have taken a rescue medication by a given timepoint if the answer to the eDiary question, 'Did you take any medication, since your last diary entry, other than the patches you applied to treat your headache?' is answered Yes at that timepoint or any preceding timepoint. The specific medication/therapy is to be recorded as a concomitant medication in the CRF.

If rescue medication use data are missing for a given timepoint and there are no "Yes" responses at a previous timepoint, missing values will be imputed using the next available value (next observation carried backward). If rescue medication data are still missing after imputation, then it will be assumed a rescue medication was not taken. For the 60-minute timepoint, if rescue medication use data are missing at 60 minutes and there are no "Yes" responses at a previous timepoint, then the subject is considered not to have taken the rescue medication by the 60-minute timepoint.

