3.2.5 Prior and Concomitant Medications Allowed During the Study

Medications that are considered necessary for the subject's welfare and are not specifically prohibited (Section 6.2.10), may be given at the discretion of the investigator. The administration of such medication must be recorded in the appropriate source document and in the electronic case report form (eCRF) for the duration of the study.

For the cluster headache to be qualifying for study medication, no medications specifically taken for the subject's headache symptoms are allowed within 24 hours prior to onset of the current cluster headache symptoms. If rescue therapy is required by the subject, rescue therapy other than a triptan or ergot is permitted at or after 20 minutes post study drug administration.

Oxygen will be provided in an "E" cylinder (680L), with a flow-rate adjustable regulator and a non-rebreather facemask.

3.2.6 Early Termination

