APPENDIX 2 SAMPLE SUBJECT eDIARY QUESTIONS

Qualifying Cluster Headache Double-Blind Period (eDiary is Activated at Visit 2)

- Are you having a cluster headache now? (Yes, No)
- How bad is your headache pain? (Mild, Moderate, Severe)
- Are you experiencing any of the following (please scroll down and select all that apply)?

Feeling Restless/Agitated? (Yes, No)

Eye redness or tearing on the same side as pain? (Yes, No)

Runny or stuffy nose on the same side as pain? (Yes, No)

Swollen eyelid on the same side as pain? (Yes, No)

Forehead and face sweating on the same side as pain? (Yes, No)

Drooping of the upper eye lid, or pupil getting smaller on same side as pain? (Yes, No)

None of the above (Yes, No)

- Did you treat your cluster headache with a triptan or ergot in the past 24 hours?
- If a non-qualifying headache:

The following text shows - **DO NOT** APPLY THE PATCHES. YOU **HAVE NOT** REPORTED a qualifying cluster headache. Please save your answers and return to the diary next time you think you are experiencing a headache.

• *If a qualifying headache:*

The following text shows - You have reported a qualifying headache. Please apply the first patch now. After applying the first patch, please respond to the question below:

Have you applied your first patch? (Yes, No)

Please apply the second patch now.

Post Patches Application Questions at: 30 min

- Where were the study drug patches applied? (Both to left arm, Both to right arm, One patch to each arm, One patch to left arm, One patch to right arm)
- Please remove the patches from your upper arm, fold in half, and discard. Press the next button once you have removed both patches.

• *Reminder* Text – You have 1 post treatment questionnaire left to complete. Please do not turn off your device. You may press next to complete this questionnaire.

Post Patches Application Questions/text at: 5, 10, 15, 20, 30, 60 min

- How bad is your headache pain? (None, Mild, Moderate, Severe)
- Did you take any medication, since your last diary entry, other than the patches you applied to treat your headache? (Yes, No)
- Do you feel able to perform your usual daily activities? (Yes/No)
- Your next assessment is due at [time]. Please keep your device with you. (at 5, 10, 15, 20, 30 minute)
- Thank you. You have answered all study related questions and your physician will contact you about setting up your final visit (at 60 minutes only)

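### Rescue status rests on one diary question about medication although the trial supplies oxygen, so oxygen use answered No can pass as relief without rescue

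*SAP*

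**What the plan says.** **What is allowed and supplied.** Protocol 3.2.5 states that "rescue therapy other than a triptan or ergot is permitted at or after 20 minutes post study drug administration". The next sentence supplies an oxygen cylinder "with a flow-rate adjustable regulator and a non-rebreather facemask". Protocol 1.1 names inhaled oxygen among the acute treatments in use.

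**What the diary is meant to capture.** Protocol 6.1.3.1 has the subject record, at each post-dose timepoint, any need for rescue *therapy*. SAP 7.2.4.4 is headed Rescue Medication/Therapy Use.

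**What the diary asks.** The only rescue item in Protocol Appendix 2, put at 5, 10, 15, 20, 30 and 60 minutes, is "Did you take any medication, since your last diary entry, other than the patches you applied to treat your headache". SAP 7.2.2 and 7.2.4.4 repeat the wording.

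**How the answer is used.** Under SAP 7.2.4.4 a subject has used rescue by a timepoint if the item "is answered Yes at that timepoint or any preceding timepoint". If the answer is still missing after imputation, "then it will be assumed a rescue medication was not taken". The specific medication or therapy goes into the CRF as a concomitant medication, but the derivation does not use that entry.

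**Where it enters.** Sustained relief requires mild or no pain at every timepoint "without the use of acute rescue medication at any time during the 60 minutes post patch administration" (SAP 7.2.3). Pain relief and pain freedom require no rescue up to the timepoint assessed (SAP 7.2.2, 7.2.4.1, 7.2.4.3). A Yes on daily activities becomes a No if rescue was used (SAP 7.2.4.5).

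**The concern.** The question is narrower than what it has to measure. The plan's concept is rescue therapy, and the one treatment it says it will provide in that context is breathed through a mask. Some subjects may not regard that as taking a medication. Such a subject can answer No in good faith, and relief produced by oxygen is then credited to the patch. The subject's CRF entry may show the oxygen, and the site may discuss it at Visit 3, yet neither changes the analysis variable.

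At stake is the no-rescue condition in the endpoints whose window runs past 20 minutes. These are relief at 30 minutes, daily activities at 30 and 60 minutes, and the sustained endpoints, which include one co-primary.

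**Working it through.** **1. Which endpoints permitted oxygen can reach.** Permitted use starts at or after 20 minutes, and pain is scored at 5, 10, 15, 20, 30 and 60 minutes.

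| Endpoint | Rescue window | Effect of oxygen use answered No |
|---|---|---|
| Relief at 5, 10, 15 min; freedom at 10, 15 min | to that timepoint | none from permitted use |
| Relief at 20 min; rescue within 20 min | to 20 min | essentially none |
| Relief at 30 min | to 30 min | direct: severe at 20, oxygen, mild or none at 30 |
| Daily activities at 30, 60 min | to that timepoint | direct |
| Sustained relief or freedom to 60 min | whole 60 min | only if every recorded score still qualifies, so in practice a relapse between scores, chiefly 30 to 60 min, that oxygen aborts |

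**2. The plan's own figure.** Inputs from SAP 5: 20% and 55%, 40 per arm, 15% dropout, two-sided 0.05, continuity-corrected chi-square. Evaluable n = 40 × 0.85 = 34. Corrected difference = 0.35 − 1/34 = 0.3206. Null SE = √(2 × 0.375 × 0.625/34) = 0.1174. Alternative SE = √((0.20 × 0.80 + 0.55 × 0.45)/34) = 0.1095. Power = Φ((0.3206 − 1.96 × 0.1174)/0.1095) = 79.6%, against the stated 80% or so. Exact power with Fisher's test, now the planned test (SAP 9.1), is 81.5%.

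**3. Relief at 30 minutes (illustration).** The documents give no rate of oxygen use, of wrong No answers, or of relief at 20 or 30 minutes. Assume 45% on drug and 80% on placebo are unrelieved at 20 minutes (the complements of 55% and 20%). Assume also that the same share m in each arm uses oxygen, improves to mild or none by 30 minutes and answers No. False successes are 45m and 80m points, so the difference falls by 35m. With no other change:

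| m | Drug | Placebo | Difference | Fisher power, 34 per arm |
|---|---|---|---|---|
| 0 | 55.0% | 20.0% | 35.0 | 81.5% |
| 5% | 57.25% | 24.0% | 33.25 | 75.1% |
| 10% | 59.5% | 28.0% | 31.5 | 67.9% |
| 20% | 64.0% | 36.0% | 28.0 | 53.8% |
| 30% | 68.5% | 44.0% | 24.5 | 44.2% |

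The power column holds for the planned size only. SAP 12 says enrollment fell short and gives no number.

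**4. Sustained relief 15–60 minutes (illustration).** Let a and b be the shares of 15-minute responders on drug and placebo who stay mild or none to 30 minutes, relapse, use oxygen, answer No, and score mild or none at 60. The net shift in favour of drug is 55a − 20b points.

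- a = b = 5%: 2.75 − 1.0 = +1.75
- a = b = 10%: 5.5 − 2.0 = +3.5
- a = b = 20%: 11.0 − 4.0 = +7.0
- a = 5%, b = 20%: 2.75 − 4.0 = −1.25

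The shift is zero when b/a = 55/20 = 2.75 and negative above that. At 34 per arm the 10% case is 34 × 0.055 = 1.9 subjects against 34 × 0.02 = 0.7. One subject is 1/34 = 2.9 points.

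**The case against.** **Safeguards exist.** Subjects are trained on the diary and reminded about rescue therapy at Visit 2 (Protocol 6.1.2), and the site reviews diary data and rescue use with them at Visit 3 (Protocol 6.1.7). This stands as a partial check. However, no document says that the training covers oxygen, and no rule lets the review change a diary No.

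**The reading of oxygen as rescue, and of No as the likely answer, is inferred.** Protocol 3.2.5 never labels oxygen as rescue; that follows from its place after the rescue sentence. Appendix 2 is headed as sample questions, though the SAP adopts the item word for word. Some subjects will count oxygen as a medication. All of this bears on the size of the error. The mismatch between therapy and medication remains.

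**Stronger readings that a reader might infer are not supported.**

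- *That both co-primaries are compromised.* Relief at 15 minutes closes before permitted rescue begins.
- *That the rescue-use endpoint is undercounted.* It covers use within 20 minutes, so permitted oxygen barely enters it, and SAP 9.2 has rescue use listed rather than summarized.
- *That the error on sustained relief favours the drug.* That needs similar rates of masked relapse in both arms. The sign turns if placebo responders have more than 2.75 times the rate of drug responders, and the documents give neither rate. The full chain of events is also demanding, so few subjects are exposed.

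**Conclusion.** The point holds as a gap in measurement and derivation. The plan permits rescue therapy and supplies oxygen, asks only about medication, and has no rule by which another record can correct a No. This rests on the text alone.

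The consequences are limited and unquantified. Relief at 30 minutes and daily activities at 30 and 60 minutes are most exposed. If misreporting is similar across arms, error in 30-minute relief tends to run against the drug, because more placebo subjects should still be in pain at 20 minutes. At an assumed 10% this costs 3.5 points. Sustained relief 15–60 minutes is exposed more narrowly, and its direction is not established. Every percentage of misreporting or relapse used above is an assumption. The point merits correction before unblinding, and it does not by itself undermine the trial.

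**What to change.** The change concerns measurement only and leaves permitted rescue as it is.

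1. **Diary.** For any subject still to be treated, reword the item to: *Since your last diary entry, did you use any medication, oxygen or other therapy to treat your headache, other than the patches?* With the SAP dated 14 April 2021 and enrollment already described as insufficient, this may reach few subjects or none.
2. **SAP 7.2.4.4.** Count rescue as used by a given timepoint if the diary answer is Yes at or before it, *or* the CRF records oxygen or another acute headache therapy started at or before it (up to 60 minutes for the sustained endpoints). Keep each endpoint's present rescue window. A blanket 60-minute rule would turn a true 15-minute responder who used oxygen at 40 minutes into a failure, contrary to SAP 7.2.2.
3. **Discrepancies.** Resolve conflicts between diary and CRF, and missing start times, by blinded query before database lock. The review meeting in SAP 8.2 is the natural place. The SAP's conventions for concomitant medications deal in dates only, and nothing shows that start times are collected. If same-day use cannot be timed, run a sensitivity analysis that counts it as rescue for the endpoints after 20 minutes.

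The cost is a few queries, some reliance on recall days after the attack, and slightly lower responder rates.
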